8.4.1.2 Injection of RGT100-PEI – Preparation

RGT100-PEI dispersion is available in 10-mL ready-to-use vials with an extractable volume of 5 mL containing 0.2 mg/mL. The vials should be stored frozen at -20°C (±5°C).

The following steps should be taken before injection:

- Thaw RGT100-PEI vial(s) to room temperature. It is recommended to administer RGT100-PEI within 4 hours.
- Draw the desired amount of RGT100-PEI from the vial into a syringe directly before the injection. Note: the vials of RGT100-PEI are for single use only and any unused dispersion has to be discarded.
- Clean the lesion and/or surrounding areas with an alcohol swab or other appropriate agent and let dry.
- For intrahepatic lesions follow routine procedure for preparation of the injection site.
- Cutaneous and subcutaneous lesions: Anesthetic agents should be avoided if possible as there is no knowledge if there may be an interaction between RGT100-PEI and an anesthetic agent. In case of severe pain, the injection site may be treated with a topical anesthetic agent.

8.4.1.3 Procedures for first injection

It is up to the Investigator to decide the best mode of accessing the tumor to inject the drug. Some examples are:

[figure not shown]
- Direct manual/visual control
- Ultrasound guidance
- CT guidance (not to be used in Germany)

Injection into liver lesions will be performed under image guidance. The total volume for injection will depend on the current DL in the dose escalation phase and on the RP2D during the expansion phase. In case several tumor lesions need to be injected, the minimum volume per injection and lesion should be 0.5 mL.

[figure not shown]
The site may utilize its routinely used needles and materials for both the cutaneous and liver lesion injections. For example: For cutaneous lesions a short needle for SC injections and for

liver lesions a 21-gauge spinal needle may be feasible for use. For liver lesion injections, local anesthesia should be considered according to the site's routine procedures together with ultrasound guidance.

[figure not shown]
Cutaneous lesions

Subcutaneous lesions

Nodal/liver lesions

The following steps should be taken for the injection:

- Determine and record the injection volume for the specific lesion.
- Using a single insertion point, inject RGT100-PEI along multiple tracks as far as the radial reach of the needle allows within the lesion to achieve even and complete dispersion. Multiple insertion points may be used if a lesion is larger than the radial reach of the needle.
- Disperse RGT100-PEI evenly and completely within the lesion by pulling the needle back without exiting the lesion. Redirect the needle as many times as necessary while injecting the remainder of the dose of RGT100-PEI. Continue until the full dose is evenly and completely dispersed.
- Use local policies to account for dead space and for flushing
- When removing the needle, withdraw it from the lesion slowly to avoid leakage or splash back of RGT100-PEI at the insertion point.
- Repeat these steps for other lesions that need to be injected. Use a new needle anytime the needle is completely removed from a lesion and each time a different lesion is injected.
- Cutaneous lesions only: apply pressure to the injection site with a sterile gauze according to routine procedures
- Intrahepatic lesions only: apply pressure to the injection site with a sterile gauze according to routine procedure.
- Dispose of all materials that have come in contact with RGT100-PEI (e.g., vial, syringe, needle, any cotton or gauze) in accordance with local institutional procedures.

The Investigator should note and record any unusual backpressure to the injection, any suspicion of leakage of injected material beyond the index lesion and any reasons why the predicted volume to be injected into an individual lesion was not achievable.

8.4.1.4 Procedures for further injections

The chosen index lesion will be injected at all scheduled visits. Only in cases where this is not possible the following lesion selection procedure will be followed:

The priority for tumor/lesion injection will be as follows:

- Previously un-injected lesions will only be selected for injection if the planned total volume for injection cannot fully be administered in the previously treated lesion (e.g., reduced lesion size). Previously un-injected tumors should be selected according to the following priority:
 1. Pre-existing lesions from the previous treatment visit that were not previously injected
 2. New lesions, newly measurable lesions and newly documented lesions which appear during the course of the study.

8.4.2 Identity of Investigational Product

The investigational medical product in this trial is RGT100-PEI, which is a double stranded 3-phosphate-RNA that binds to RIG-I (RGT100); *in vivo* JetPEI™ is the delivery vehicle. RGT100-PEI will be applied intratumorally/intralesionally. RGT100-PEI will be provided as ready-to-use formulation in 10-mL vials.

8.4.3 Packaging and Labelling

The manufacture and labelling of RGT100-PEI meets the requirements of Good Manufacturing Practice and will be performed at the manufacturing site and at the drug supplier.

8.4.4 Method of Assigning Subjects to Treatment Groups

Once written informed consent has been obtained, the subject will be issued with a unique screening number, which will be recorded in a Screening Log. Following screening, subjects who meet all the inclusion criteria and none of the exclusion criteria will be enrolled in to 1 of the groups of the study, and sequentially assigned to a dose cohort of RGT100-PEI during the dose escalation phase or to the RP2D for the expansion phase.

If appropriate, and with prior approval from the Sponsor or their designee, subjects who fail screening, or who pass screening but have not been treated, may be re-screened for subsequent cohorts.

8.4.5 Subject Enrolment and Slot Allocation

Slot allocation will be based on competitive enrolment. However, if there are any pre-allocated slots, the INCR Project Lead (PL) will notify the site personnel of the pre-allocated slots prior to each cohort review/opening. Another review of slots allocation will be done during Safety Review calls and Dose Escalation Meetings.

The site will notify the INCR PL via email as soon as a subject has been identified. The PL maintains a tracking overview of all communicated potential study subjects and will confirm the current status back to the site.

Sites are expected to identify potential subjects prior to the Dose Escalation Meetings and to be able to start consenting/screening procedures directly following the slot confirmation.

The email notification must include the following information:

- Subject initials and/or local tracking number (depending on site/local regulations)

- Tumor type
- Year of birth
- Planned Consent / Screening date and
- Anticipated start date

A slot will not be held for any subject if the above information is not available.

Ultimately, in case of dispute or unclarity, the INCR Project Lead (PL), in discussion and agreement with Rigontec, is in charge of slot allocation and has final say.

If a site does not confirm that their identified and slot allocated subject has consented within 5 business days of the cohort opening, the unclaimed slot will become competitive (unless otherwise agreed in writing between the site and INCR PL). The INCR PL will notify all open sites of the availability of competitive slots and all sites will be notified the same day when a competitive slot is claimed. This process will continue until the cohort is filled.

This information will be reiterated at the safety meetings or calls.

Once a subject has successfully completed screening, the Enrolment form must be completed and sent as an attachment to ^{PPD} [REDACTED]. The INC Medical Monitor will check, evaluate the enrolment form and approve or reject to assure that only eligible subjects will be enrolled into the trial and into the correct cohort. The subject number, treatment and dose will be confirmed within 12 (business) hours per email.

8.4.6 Selection of Doses in the Study

The concentration of the RGT100-PEI particles in the injection dispersion is fixed to 0.2 mg/mL to achieve stable complexes. Volumes of RGT100-PEI will be escalated to provide total doses of, for example, 0.2, 0.4, 0.6, and 0.8 mg per injection.

The planned starting dose of 1 mL (0.2 mg) for the dose escalation phase of the study is based on pre-clinical data (refer to [Section 6.4](#) for dose justification). To date there are no human data for RGT100-PEI.

Subsequent dose escalation will be based on the safety findings of the previous dose following review by the SRC (refer to [Section 8.1.1](#) for dose escalation details).

8.4.7 Dose-limiting Toxicity

The DLTs and MTD are defined using the NCI CTCAE version 4.03.

Dose-limiting toxicities will be drug-related toxicities (considered related or possibly related to) and graded using NCI CTCAE version 4.03 occurring during the DLT period and include:

- Non-hematologic toxicity \geq grade 3 (except diarrhea, nausea, and vomiting unless lasting >3 days despite optimal supportive care)
- Confirmed (with a second measurement after 24 hours) non-hematologic appropriately graded laboratory findings of grade ≥ 3 that were \leq grade 1 at baseline
- Hematologic toxicity:

- Grade 4 neutropenia ≥ 5 days, or grade 3 neutropenia with fever (fever is $> 38.4^{\circ}\text{C}$)
- Grade 4 thrombocytopenia, or grade 3 thrombocytopenia lasting > 7 days or with bleeding
- Any other toxicity assessed as related to RGT100-PEI, and which, in the opinion of the study Investigator(s) and the Sponsor physician constitutes a DLT

The DLT period will be 4 weeks. Evaluation of the available safety data over this DLT period will be required from at least 3 subjects per DL and per Group (A or B) before a decision is made whether to enroll additional subjects at the same, or the next DL.

Note: Subjects withdrawn from the study before the completion of the DLT period for reasons other than DLT will be replaced.

During dose escalation, escalation to the next DL will occur only if the safety and tolerability (including DLTs) data are acceptable as determined during the dose escalation meetings by the SRC. If any change is made to the grade or causality of an AE during the study that may alter its DLT status, the Sponsor and SRC must be informed immediately as this may affect dose escalation decisions.

The following toxicities will not be considered as DLTs:

- Grade 3 AE of tumor flare (defined as local pain, irritation, or rash localized at sites of known or suspected tumor)
- Grade 3 irAE that resolves to grade ≤ 1 within 7 days.

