7.2 Endpoints

The primary endpoints of the study are:

- Incidence and severity of treatment-related adverse events (AEs) and laboratory abnormalities, graded according to National Cancer Institute Common Terminology Criteria for Adverse Events (NCI CTCAE) version 4.03 criteria
- Occurrence of serious adverse events (SAEs)
- Occurrence of treatment discontinuation due to treatment-related AEs
- Incidence and severity of dose-limiting toxicities (DLTs)

The secondary endpoint of the study is:

- Objective response rate as evaluated radiologically using immune-related Response Evaluation Criteria in Solid Tumors (irRECIST)

The exploratory endpoints of the study are:

- Type of cytokine release in plasma
- Plasma concentrations of RGT100-PEI and, where feasible, standard PK parameters
- Presence of predictive biomarkers of tumor responses*
- Evidence of immune infiltration of injected tumors*

*These exploratory objectives will be evaluated in a separate sub-study. Results of these exploratory investigations will not be presented as part of the main Clinical Study Report.

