A standard 3 + 3 design ([Table 1](#)) will be used for dose escalation (3 subjects per DL group, with the potential to add an additional 3 subjects to a DL group if toxicity is observed).

Table 1: Standard 3+3 Dose Escalation Scheme

Number of Subjects with a DLT at a Given Dose Level (during the DLT period)	Action
0 out of 3 subjects experience a DLT	Escalate to the next DL
1 out of 3 subjects experiences a DLT	Enter 3 additional evaluable subjects at the current DL for a total of 6 evaluable subjects
1 out of 6 subjects experiences a DLT	Escalate to the next DL

2 or more subjects (up to 6 subjects) experience a DLT	Dose escalation will be stopped (at this DL the MTD has been exceeded or declared)
--	--

Abbreviations: DL = dose level; DLT = dose-limiting toxicity; MTD = maximum tolerated dose.

If more than 2 subjects experience a DLT at a particular DL, a lower (or intermediate) DL may be explored to better define the MTD. Refer to [Section 8.4.6](#) for DLT definition and [Section 8.4.7](#) for MTD definition.

Approximately 9 to 24 subjects will be treated in each group during the dose escalation. All types of tumors that are accessible for intratumoral/intralesional injection may be treated in the dose escalation part of the study.

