10.4.1.3 Assessment of Severity

Severity of AEs refers to the extent to which an AE affects the subject’s daily activities. The severity of AEs and toxicities must be graded by the Investigator according to the NCI CTCAE version 4.03. The NCI CTCAE version 4.03 can be found at <http://www.oncology.tv/SymptomManagement/NationalCancerInstituteUpdatesCTCAEto403.aspx>.

Grade 1	Mild; asymptomatic or mild symptoms; clinical or diagnostic observations only; intervention not indicated.
Grade 2	Moderate; minimal, local or noninvasive intervention indicated; limiting age-appropriate instrumental activities of daily living (ADL)*.
Grade 3	Severe or medically significant but not immediately life-threatening; hospitalization or prolongation of hospitalization indicated; disabling; limiting self-care ADL**.
Grade 4	Life-threatening consequences; urgent intervention indicated.
Grade 5	Death related to AE.

*Instrumental ADL refer to preparing meals, shopping for groceries or clothes, using the telephone, managing money, etc.

**Self-care ADL refer to bathing, dressing and undressing, feeding self, using the toilet, taking medications, and not bedridden.

The term “severity” is used to describe the intensity of an AE. This is not the same as “serious”. Seriousness, not the severity, serves as the guide for defining regulatory reporting obligations. Notwithstanding this differentiation, AEs of severity grade 4 or 5 (life-threatening or fatal) will meet the criteria for seriousness and will thus qualify as SAEs/irAEs.

If there is a change in severity of an AE, it will be captured as 1 AE, with the highest severity grade recorded.

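### Section 8.4.7 makes febrile grade 3 neutropenia a listed DLT but leaves febrile grade 4 neutropenia of under 5 days to judgement, because the fever limb says grade 3 and not grade ≥ 3

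*Combined protocol and SAP*

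**What the plan says.** Section 8.4.7 (Dose-limiting Toxicity) defines DLTs as drug-related toxicities in a 4-week period and gives a list of what they include.

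- **Neutropenia** has two limbs: grade 4 for at least 5 days, "or grade 3 neutropenia with fever", with fever meaning above 38.4 °C. The fever limb has no minimum duration, and the grade 4 limb does not mention fever.
- **Thrombocytopenia** is built differently: "Grade 4 thrombocytopenia, or grade 3 thrombocytopenia lasting" more than 7 days or with bleeding. Grade 4 counts there at any duration.
- **The two bullets set at grade 3 or above** are limited to non-hematologic toxicity and non-hematologic laboratory findings.
- **The last bullet** admits any other related toxicity that "in the opinion of the study Investigator(s) and the Sponsor physician constitutes a DLT".

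The same section says that "escalation to the next DL will occur only if the safety and tolerability (including DLTs) data are acceptable" to the SRC. Section 10.4.1.3 adds that "AEs of severity grade 4 or 5 (life-threatening or fatal) will meet the criteria for seriousness".

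The count matters because section 7.2 makes "Incidence and severity of dose-limiting toxicities (DLTs)" a primary endpoint, Table 1 in section 8.1.1 acts on the number of subjects with a DLT, and section 11.1.6 tabulates subjects with and without DLT and names DLTs as the basis for choosing the RP2D.

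**The concern.** A DLT list should not rank a worse event below a milder one. Here a subject with fever and a grade 3 neutrophil count has an automatic DLT. A subject with fever and a grade 4 count that recovers within 1 to 4 days does not, unless two parties agree to call it one.

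The missing symbol looks unintended. The section writes grade 3 or above explicitly where it means that. Elsewhere it uses bare grade 3 to mean exactly grade 3: the exemption for a grade 3 immune-related event that resolves within 7 days would also exempt grade 4 events if bare grade 3 meant 3 or worse. The fever limb therefore cannot safely be read as covering grade 4.

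At stake is a single count in a 3+3 design, where one subject can change the action. There is also a consistency risk: sites, or Groups A and B, could classify the same event differently when its status rests on opinion.

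**Working it through.** The plan states no figure to reproduce on this point. The check applies the rule as written and as corrected, then carries the difference through Table 1.

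**Step 1. The two rules** (inputs from section 8.4.7)

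- As written: (grade 4 and duration ≥ 5 days) or (grade 3 and fever).
- As corrected: (grade 4 and duration ≥ 5 days) or (grade ≥ 3 and fever).

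| Neutropenia, drug-related | Duration | Fever at that grade | As written | As corrected |
|---|---|---|---|---|
| Grade 3 | any | no | not listed | not listed |
| Grade 3 | any | yes | DLT | DLT |
| Grade 4 | under 5 days | no | not listed | not listed |
| **Grade 4** | **under 5 days** | **yes** | **not listed** | **DLT** |
| Grade 4 | 5 days or more | yes or no | DLT | DLT |

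Only one row changes. If fever was also present while the count was at grade 3, the fever limb is met as written. The gap is therefore fever only while at grade 4.

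**Step 2. Table 1, if the event is not counted and the subject stays evaluable**

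| Cohort | Counted | Not counted |
|---|---|---|
| 3 subjects, no other DLT | 0 + 1 = 1/3: add 3 subjects | 0/3: escalate |
| 6 subjects, one other DLT | 1 + 1 = 2/6: stop | 1/6: escalate |

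The second contrast falls at the row "1 out of 6 subjects experiences a DLT", where the action is to escalate. In the first contrast, a counted event followed by no DLT in the three added subjects gives 1/6 and escalation as well. What is lost there is the information from three more subjects at that level.

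**Step 3. Replacement** (section 8.3.4.2)

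Under section 8.4.9.4, grade 4 toxicity interrupts dosing until recovery to grade 1 or lower, or to baseline. If the subject missed more than 2 injections (Group A) or more than 1 (Group B) because of an event not classed as a DLT, the subject would be replaced for DLT evaluation. The Step 2 counts do not then apply as shown; the replacement's outcome takes the place.

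**Step 4. What could follow for the MTD** (section 8.4.8; doses of 0.2, 0.4, 0.6 and 0.8 mg from Table 2)

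The MTD is one level below the stopped level. For an event at DL3 in a cohort of 6 with one other DLT:

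- Counted: DL3 stops and the MTD is DL2, 0.4 mg.
- Not counted: DL4 opens to 3 to 6 subjects, subject to SRC agreement. If DL4 stops, the MTD is 0.6 mg, a difference of 0.6 − 0.4 = 0.2 mg or one level. If DL4 has at most 1/6, no MTD is reached.

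Three conditions limit this:

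1. The cohort must have one other DLT.
2. The next lower level, if only 3 subjects were treated there, is expanded to 6 where necessary and could itself fail.
3. The SRC may choose an intermediate level.

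For a stop at DL2, 0.2 mg is a tested level in Group A only, because Group B starts at DL2.

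**The case against.** The strongest reply is that the protocol handles the event by other means. The DLT list is introduced as inclusive, and its last bullet exists for such cases. A grade 4 event is an SAE, reportable within 24 hours (section 10.4.4.3), and it interrupts dosing. Bi-weekly safety calls run during escalation, and the SRC judges all safety data, not only the DLT count. An accompanying non-hematologic related toxicity of grade 3 or above would generally count by itself. Neutropenia is not among the potential risks in section 6.6, and section 8.1.1 expects a maximum feasible dose to be reached before an MTD. If no MTD is reached, section 8.4.8 selects the RP2D on integrated data. All of this stands and makes the practical risk modest. It does not repair the rule: these safeguards rest on judgement, while the milder event needs none.

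Three stronger readings are tempting, and the documents do not support them.

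- **That the AE recording rule closes off the grade 3 phase.** For a change in severity, section 10.4.1.3 says "it will be captured as 1 AE, with the highest severity grade recorded". A reader might infer that an episode passing through febrile grade 3 would lose its DLT status once recorded as grade 4. That rule governs AE capture, not DLT adjudication. The DLT limbs depend on time spent at a grade, so adjudication needs dated laboratory values, where a febrile grade 3 phase would remain visible.
- **That the MTD would be wrong by a fixed amount.** The conditions in Step 4 of the working, and replacement in Step 3, rule out any unconditional figure.
- **That escalation would probably be unsafe.** The documents give no rate for neutropenia, so no probability follows from them.

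**Conclusion.** The point holds as a fault in a stated decision rule. As written, section 8.4.7 misorders severity in one case: related grade 4 neutropenia of under 5 days, febrile only while at grade 4. The event is not a listed DLT and depends on the last bullet.

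The size is one subject in the Table 1 count, on the assumptions that the last bullet is not used and the subject stays evaluable. One subject is enough to change the action at 0/3 versus 1/3 and at 1/6 versus 2/6. Any effect on the MTD or the RP2D is conditional and cannot be quantified further. A missed event is unlikely, so this is a correction that should be made, not evidence that the escalation is unsafe.

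**What to change.** In section 8.4.7, change the fever limb to: grade ≥ 3 neutropenia with fever (> 38.4 °C). Classify DLTs on that wording for Table 1 decisions, and use the same wording for the DLT tabulations in section 11.1.6.

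The change is one symbol in the definition and requires no extra data or visits. Its only downside is a possibly slightly higher DLT count, which errs on the cautious side.

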8.4.8 Maximum Tolerated Dose, Maximum Feasible Dose, and RP2D

The MTD is defined as 1 DL below the DL where ≥ 2 of 6 subjects in a group experience a DLT for RGT100-PEI during the DLT period of 4 weeks. Maximum tolerated dose will be determined following discussion of all the relevant toxicity data by the SRC during the dose escalation meetings after each dose escalation step (refer to [Section 10.5](#) for SRC details).

If ≤ 1 of 6 subjects in all dose levels experience a DLT, then an MTD will not have been reached in this group. In this case, the RP2D will be selected based on integrated evaluation of safety, tolerability, clinical benefit, and pharmacodynamic data, for all DLs tested.

Once the MTD has been defined, dosing at a higher dose must not occur in this group. Once the MTD has been exceeded, the cohort at the next lowest DL will be expanded to 6 subjects if necessary and only 3 subjects were involved before. The SRC are free to decide on an intermediate DL.

The MFD is the highest dose volume that is safe and tolerable, and is feasible for intralesional/intratumoral injection in the respective group. The MFD may be lower than the MTD. The MTD (or MFD if lower than MTD) will define the RP2D to be used in the expansion phase of the study.

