8.1.1 Dose Escalation Phase

This phase of the study will investigate increasing DLs of RGT100-PEI to determine the MTD or maximum feasible dose (MFD). The MFD is the highest dose volume that is safe and tolerable, and is feasible for intralesional/intratumoral injection. The MFD may be lower

than the MTD. The MTD (or MFD if lower than MTD) will define the RP2D to be used in the expansion phase of the study.

RGT100-PEI will be at a fixed concentration of 0.2 mg/mL and dose escalation will be based on the total volume of RGT100-PEI injected per subject. The planned DLs to be investigated in this phase of the study are:

- DL1: 0.2 mg = 1 mL
- DL2: 0.4 mg = 2 mL
- DL3: 0.6 mg = 3 mL
- DL4: 0.8 mg = 4 mL*

*Dose escalation may continue if deemed appropriate by the Safety Review Committee (SRC) (refer to [Section 10.5](#) for SRC details). The corresponding next dose levels beyond the above and the supporting safety data to continue will be described within a substantial amendment to this protocol which will only be implemented once approval has been received.

It is not expected that a MTD will be reached at the proposed dose levels. It is more likely that a maximum feasible dose will be reached before the MTD, defined as the maximum volume which can be injected into a lesion. Experience with other compounds which are also injected intratumorally/intralesionally was taken into consideration when planning the proposed dose levels and the initially proposed highest dose. However according to the nature of a phase I trial the maximum tolerable and/or feasible dose level are yet unknown and cannot be predicted.

The specific properties of RGT100-PEI being an immune-modulating drug is taken into consideration and safety will be closely monitored to detect any early signs of toxicity in general and dose limiting toxicities in particular.

For each DL the second and subsequent subject treated will start treatment at least 7 days following the first subject's injection to allow initial assessment of safety data by the treating Investigator and to report any serious potential safety concerns such as DLTs.

Group A will commence dosing first. Group B will commence dosing once DL2 has been shown to be safe and well tolerated in Group A subjects. Dosing will then commence at DL2 for Group B.

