8.4.9 Selection and Timing of Dose for Each Subject

8.4.9.1 Dose Escalation Phase

The planned DLs to be investigated are presented in Table 2 below.

Table 2: Dose Levels for RGT100-PEI Dose Escalation

Dose Level	RGT100-PEI Dose	Volume of RGT100-PEI to be Injected
1	0.2 mg	1 mL
2	0.4 mg	2 mL
3	0.6 mg	3 mL
4	0.8 mg	4 mL

RGT100-PEI will be administered by intratumoral/intralesional injection. A dose escalation meeting with the SRC (refer to [Section 10.5](#) for SRC details) will be held to evaluate a dose escalation after all subjects in a DL per group have completed the DLT period.

Group A: Dosing for Group A (cutaneous lesions) will start first. The total dose will be administered each on 2 separate days of every week (Mondays and Thursdays or Tuesdays and Fridays) for a maximum of 4 weeks.

Group B: Dosing for Group B (liver lesions) will start once DL2 has proven to be safe in Group A. Dosing in Group B will then start at DL2. The total dose will be administered on 1 day of every week for a maximum of 4 weeks.

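### If Group B (liver) stops at its starting level, DL2, the 8.4.8 definition points to DL1 as its MTD although no Group B subject has received DL1; the lower-level sentence in 8.1.1 also does not match the Table 1 stop

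*Combined protocol and SAP*

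**What the plan says.** Sections 8.1.1 and 8.4.9.1 open Group B once DL2 has been found safe in Group A: "Dosing will then commence at DL2 for Group B" and "Dosing in Group B will then start at DL2". No DL1 cohort is planned for Group B.

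Table 1 in 8.1.1 stops escalation when "2 or more subjects (up to 6 subjects) experience a DLT". The sentence below the table reads: "If more than 2 subjects experience a DLT at a particular DL, a lower (or intermediate) DL may be explored".

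Section 8.4.8 contains four relevant statements:
- "The MTD is defined as 1 DL below the DL where" at least 2 of 6 subjects in a group have a DLT during the 4-week DLT period. The SRC determines the MTD after discussing the toxicity data.
- Once the MTD has been exceeded, the cohort at the next lowest level "will be expanded to 6 subjects if necessary and only 3 subjects were involved before".
- On levels between the planned ones, it leaves the choice open: "The SRC are free to decide on an intermediate DL".
- On the expansion dose, it says: "The MTD (or MFD if lower than MTD) will define the RP2D to be used in the expansion phase of the study".

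Section 8.4.7 asks for DLT-period data from at least 3 subjects per dose level and per group before deciding whether to enrol more subjects at the same or the next level. Section 8.1.2 requires a safety report, a protocol amendment and acceptance of the RP2D by authorities before expansion starts.

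**The concern.** The MTD definition assumes that the level below the stopping level has already been tested in the same group. That holds in Group A for any stop above DL1. It does not hold in Group B for a stop at its first level.

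Determining the RP2D is a primary objective. If Group B stops at DL2, following 8.4.8 as written would give a liver MTD, and hence a liver RP2D, with no liver DLT data at that dose.

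Group A's experience at DL1 is not a substitute. Group A receives injections into cutaneous, subcutaneous or nodal lesions twice a week; Group B receives injections into liver lesions once a week (8.4.1, 8.4.9.1). Section 6.4 states that local toxicity of direct liver injection was not studied and is extrapolated from intravenous data. After two liver DLTs at DL2, whether the liver tolerates half that dose is the question the trial would need to answer.

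The 8.1.1 mismatch adds to this. The one sentence that speaks of going to a lower level is silent on a stop with exactly 2 DLTs.

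**Working it through.** **Rule trace for a Group B stop at DL2**

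| Rule | Effect after 2 or more DLTs at DL2 in Group B |
|---|---|
| Table 1 | Escalation stops; the table gives no step down |
| 8.4.8, MTD definition | Points to DL1 (0.2 mg); Group B subjects treated there: 0 |
| 8.4.8, expansion to 6 | Worded for a cohort that already has 3 subjects; Group B has no cohort below DL2 |
| 8.1.1, lower or intermediate level | Optional, and worded for 3 or more DLTs |
| 8.4.7, 3 subjects per level and group | Governs enrolment at the same or next level, not the level named as MTD |
| 8.4.8, intermediate level | SRC discretion; does not require liver data at the level chosen |

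No row requires Group B subjects at the level that is named.

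**Planned numbers.** The 9 to 24 per group agrees with 3 levels × 3 = 9 (Group B, DL2 to DL4) and 4 levels × 6 = 24 (Group A, DL1 to DL4).

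**How often the situation would arise.** The documents give no DLT rates, so the true rate p at DL2 in Group B is an assumption. Write b(x) for the binomial probability of x DLTs in 3 subjects.

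- P(stop) = b(2) + b(3) + b(1) × [1 − b(0)]
- P(stop with exactly 2 DLTs) = b(2) + b(1) × b(1)

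| p | P(stop) | P(stop with exactly 2) | Share of stops |
|---|---|---|---|
| 0.10 | 0.028 + 0.243 × 0.271 = 0.0939 | 0.027 + 0.243² = 0.0860 | 92% |
| 0.20 | 0.104 + 0.384 × 0.488 = 0.2914 | 0.096 + 0.384² = 0.2435 | 84% |
| 0.30 | 0.216 + 0.441 × 0.657 = 0.5057 | 0.189 + 0.441² = 0.3835 | 76% |

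The last column shows how often the 8.1.1 sentence would be silent. It does not show how often a lower level would be barred.

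**What a Group B cohort at DL1 would add.** Suppose 6 evaluable subjects are required before DL1 is declared the MTD. For an assumed true DL1 liver rate p, the chance of 2 or more DLTs is 1 − (1 − p)⁶ − 6p(1 − p)⁵:
- p = 0.05: 1 − 0.7351 − 0.2321 = 0.033
- p = 0.10: 1 − 0.5314 − 0.3543 = 0.114
- p = 0.20: 1 − 0.2621 − 0.3932 = 0.345

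The ordinary 3+3 step, which does not fill to 6 after 0 of 3, gives 3%, 9% and 29%.

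One-sided 95% exact upper bounds on the DLT rate are 1 − 0.05^(1/6) = 39% for 0 of 6, and 58% for 1 of 6. The information is modest, but the present rule seeks none.

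**Subjects needed.** At most 6 at DL2 plus 6 at one lower level = 12 evaluable, below the planned 24.

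**The case against.** The case for leaving the text alone has several parts.

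- **The MTD is not set mechanically.** The SRC determines it after discussion and may pick an intermediate level. Meeting procedures are left to the SRC Charter (10.5), which is not available. This stands: DL1 is where the definition points, not an automatic outcome. But the discretion does not oblige anyone to obtain liver data.
- **The 8.1.1 sentence is permissive.** A reader might infer that a lower level may not be explored after exactly 2 DLTs. The text does not say so: it is an option, it contains no *only if*, and the SRC's freedom to choose an intermediate level has no DLT-count condition. The mismatch with Table 1 is a drafting inconsistency.
- **The definition says 2 of 6.** A stop at 2 or 3 of the first 3 does not literally meet it. At the assumed rates such stops are 0.028/0.0939 = 30%, 0.104/0.2914 = 36% and 0.216/0.5057 = 43% of DL2 stops. Read that strictly, 8.4.8 names no MTD in those cases, so Group B still lacks a rule. Read by its purpose, the expansion sentence shows an aim of 6 subjects at the candidate MTD. It does not say to open a new Group B cohort.
- **Later checks exist.** A reader might infer that expansion subjects would be dosed at an untested liver dose. Section 8.1.2 does not allow that without a justified RP2D, an amendment and acceptance by authorities. This limits harm, but supplies no data.
- **The event is unexpected and the fallback is a step down.** Section 8.1.1 does not expect an MTD at the planned levels, and DL1 is half the dose and already given in Group A. Both are true, but the same section says the tolerable dose cannot be predicted.

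**Conclusion.** The gap is real and confined to one contingency. If 2 or more Group B subjects have a DLT at DL2, the written definition points to DL1 with 0 Group B subjects treated there, and nothing requires liver data before that level becomes the group's MTD and RP2D. This follows from the text and rests on no assumed rate. The likelihood of the contingency (9% to 51%) rests wholly on assumed DL2 rates of 10% to 30%.

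The mismatch between 8.1.1 and Table 1 is a separate, smaller inconsistency. The documents support neither the reading that DL1 would be imposed automatically nor the reading that a lower level is barred after exactly 2 DLTs. The text should be corrected because a primary objective depends on it and the correction is cheap. SRC judgement and regulatory review keep it from being a critical safety defect.

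**What to change.** In 8.1.1, change the condition for exploring a lower or intermediate level from *more than 2 subjects* to *2 or more subjects*, to match Table 1.

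In 8.4.8, add:
1. No MTD or RP2D is declared for a group at a dose level without evaluable subjects of that group.
2. If Group B stops at DL2, the SRC either opens DL1 (or an intermediate level) in Group B under the same 3+3 rules, or closes Group B without an RP2D.
3. If a lower level is opened, 6 evaluable Group B subjects are assessed there over the 4-week DLT period before it is declared the MTD.
4. If the lower level also has 2 or more DLTs, no Group B MTD is declared.

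The Group B start at DL2 is unchanged, and a stop there does not compel further liver dosing.

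The cost is text edits to two sections. Up to 6 further Group B subjects and their DLT periods are needed only after a DL2 stop and only if the SRC continues. For one lower level the Group B total is at most 12, within the planned 9 to 24. If Group B does not stop at DL2, no subjects are added.
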